9.4. Study Population

The ITT analysis set (see Section 9.2.1) will be used for all study population summaries unless otherwise specified. Summaries will be presented by treatment group and for all patients.

9.4.1. Patient Disposition

Data from patients screened; patients screened but not randomized and reason for not randomized; patients who are randomized; patients randomized but not treated; patients in the ITT, safety, and other analysis sets; patients who complete the study; and patients who withdraw from the study will be summarized using descriptive statistics. Data from patients who withdraw from the study will also be summarized by reason for withdrawal using descriptive statistics.

9.4.2. Demographic and Baseline Characteristics

Patient demographic and baseline characteristics, including medical history, prior medications and therapies, and ECG findings will be summarized using descriptive statistics. For continuous variables, descriptive statistics (number [n], mean, SD, median, minimum, and maximum) will be provided. For categorical variables, patient counts and percentages will be provided. Categories for missing data will be presented if necessary.

Treatment groups will be compared for all continuous variables, using an analysis of variance (ANOVA) with treatment group as a factor. The categorical variables of patient sex and race will be summarized using descriptive statistics for each variable category. Missing categories will be presented if necessary. Treatment groups will be compared for all categorical variables using a Pearson's chi-square (or Fisher's exact test if cell sizes are too small).

9.5. Efficacy Analysis

For the purpose of this study, a CH attack will be endorsed when the following situations occur:

1. Severe or very severe unilateral orbital, supraorbital, and/or temporal pain lasting 15 to 180 minutes
2. Either or both of the following:
 - at least 1 of the following symptoms or signs, ipsilateral to the headache:
 - conjunctival injection and/or lacrimation
 - nasal congestion and/or rhinorrhea
 - eyelid edema
 - forehead and facial sweating

- forehead and facial flushing
- sensation of fullness in the ear
- miosis and/or ptosis
- a sense of restlessness or agitation

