3. STUDY DESIGN

3.1. General Design and Study Schematic Diagram

This is a 13-week, multicenter, randomized, double-blind, double-dummy, placebo-controlled, parallel-group study to compare the safety, and efficacy of 2 dose regimens of fremanezumab versus placebo in adult patients for the prevention of ECH. The study will consist of a screening visit, a run-in period lasting at least 1 week (+3 days), and a 12-week double-blind treatment period. During the course of any CH attack, patients will be allowed to use acute medications to treat acute headaches, as needed (PRN).

Patients will complete a screening visit (visit 1) after providing written informed consent, and eligible patients will enter a run-in period lasting at least 1 week (+3 days) during which they will enter baseline CH attack information into an electronic diary device daily. Patients will return to the study center after completing the run-in period (visit 2 [week 0]). Patients who had at least 7 CH attacks during the run-in period and who continue to meet eligibility criteria (including entry of CH attack information in an electronic diary demonstrating compliance for 85% of days during the run-in period) will be randomly assigned at visit 2 (week 0) in a 1:1:1 ratio to 1 of 3 treatment groups as follows:

- fremanezumab 900-mg iv loading dose group: fremanezumab at 900 mg administered via an approximately 1-hour iv infusion at visit 2 (week 0) followed by fremanezumab at 225 mg administered as single sc injections (225 mg/1.5 mL) at visits 3 and 4 (weeks 4 and 8, respectively)
- fremanezumab 675-mg sc quarterly group: fremanezumab at 675 mg administered as 3 sc injections (225 mg/1.5 mL) at visit 2 (week 0) followed by placebo administered as single sc injections at visits 3 and 4 (weeks 4 and 8, respectively)
- placebo group: placebo administered via an approximately 1-hour iv infusion and as 3 sc injections at visit 2 (week 0) followed by placebo administered as single sc injections at visits 3 and 4 (weeks 4 and 8, respectively)

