6.1. Electronic Diary Device

Efficacy endpoints related to CH attacks will be derived from data collected daily using an electronic diary device. Eligible patients will receive comprehensive training at screening from the investigational site personnel on the use of the electronic diary device. Investigational site personnel will also instruct patients on the requirement for timely and daily completion of the electronic diary.

Patients will complete electronic headache diary entries with questions about the previous day, starting from the day after the screening visit through the end of treatment (EOT)/early withdrawal visit. The electronic headache diary device will allow entry of headache information for up to 2 days after a given day.

Patients who report a CH attack will answer questions about the attack (ie, occurrence and number of CH attacks, duration of CH attack[s], severity of CH attack[s], and acute CH-specific medication and oxygen use). The last day of the run-in period should be reported in the morning of the visit day.

Patients will be asked about their performance at work or at school on CH attack-free days. Additional details can be found in the electronic diary device training manual.

If a patient fails to complete the diary for the preceding day, the patient will be prompted to enter the missed day's information the next time he/she accesses the electronic diary provided no more than 2 days have elapsed since completion of that day. If more than 2 days have elapsed since completion of a diary day, the patient will not be allowed to enter diary information for that day, and it will be considered a missed day.

If a CH is reported, then CH intensity will be subjectively rated by the patient as follows:

- Mild
- Moderate
- Severe
- Very severe

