9.5.1. Primary Endpoint

The primary efficacy endpoint of this study is the mean change from baseline (run-in period) in the weekly average number of CH attacks during the 4-week period after administration of the first dose of the IMP, ie, based on week 0 to 4 data.

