3.1 Cluster headache

Diagnostic criteria:

- A) at least 5 attacks fulfilling criteria B-D
- B) severe or very severe unilateral orbital, supraorbital and/or temporal pain lasting 15 to 180 minutes (when untreated)¹
- C) either or both of the following:
 - 1) at least 1 of the following symptoms signs, ipsilateral to the headache:
 - a) conjunctival injection and/or lacrimation
 - b) nasal congestion and/or rhinorrhea
 - c) eyelid edema
 - d) forehead and facial sweating
 - e) forehead and facial flushing
 - f) sensation of fullness in the ear
 - g) miosis and/or ptosis
 - 2) a sense of restlessness or agitation
- D) attacks have a frequency of between 1 every other day and 8 per day for more than half of the time when the disorder is active
- E) not better accounted for by another ICHD 3-beta diagnosis

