3.1.2 Chronic cluster headache

Diagnostic criteria:

- A) Attacks fulfilling criteria for 3.1 Cluster headache and criterion B
- B) Occurring without a remission period or with remissions lasting < 1 month, for ≥ 1 year

¹ During part (but less than half) of the time course of 3.1 Cluster headache, attacks may be less severe and/or of shorter or longer duration.

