6. EFFICACY ANALYSIS

6.1. General

The FAS will be used for all efficacy analyses unless otherwise noted. Analyses of the primary and secondary endpoints will be repeated for the PP analysis set [REDACTED].

For data not collected daily, baseline is the last observed data before the administration of the first dose of the IMP. For data collected daily in the e-diary, baseline will be derived from the run-in period (including days from the informed consent up to the day prior to the first dose of the IMP administration). Details are provided in Section 6.1.3. The efficacy baseline value derived from the run-in period are

- number of CH attacks
- number of CH attacks of at least severe severity
- number of days with use of cluster-specific acute headache medication (triptans and ergot compounds)
- number of days with use of any acute headache medication
- number of days oxygen is used
- severity of CH attacks

Summaries will be presented by treatment group as randomized unless otherwise noted. In addition to inferential statistics, descriptive statistics will be presented by-visit or by-analysis-window summaries.

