6.2. Primary Efficacy Endpoint and Analysis

6.2.1. Definition

The primary efficacy endpoint of this study is the mean change from baseline (run-in period) in the weekly average number of CH attacks during the 4-week period after administration of the first dose of the IMP.

CH attacks will be derived from the e-diary data as described in Section 6.1.1. The analysis will be based on the weeks 1 to 4 analysis window, which will be derived using the algorithm described in Section 6.1.3. Missing data handling methods are provided in Section 6.1.4.1.

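### The 15-minute floor in the attack definition omits the diagnostic qualifier for untreated attacks, so read literally a genuine attack aborted early by permitted acute treatment is not counted

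*Protocol*

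**What the plan says.** Protocol Section 9.5, repeated in the synopsis under the analysis of the primary endpoint, sets the rule for accepting an attack. Criterion 1 is "Severe or very severe unilateral orbital, supraorbital, and/or temporal pain lasting 15 to 180 minutes". Criterion 2 is an ipsilateral sign, restlessness or agitation, or both.

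Appendix I reproduces the diagnostic criteria. Its criterion B for cluster headache reads "severe or very severe unilateral orbital, supraorbital and/or temporal pain lasting 15 to 180 minutes (when untreated", with the bracket closing there. The Appendix I footnote adds that for less than half of the course "attacks may be less severe and/or of shorter or longer duration".

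On treatment, Protocol Section 3.1 says "During the course of any CH attack, patients will be allowed to use acute medications to treat acute headaches, as needed (PRN". On data, Section 6.1 has the diary collect "occurrence and number of CH attacks, duration of CH attack[s], severity of CH attack[s], and acute CH-specific medication and oxygen use".

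The primary endpoint in Section 9.5.1 is the "mean change from baseline (run-in period) in the weekly average number of CH attacks during the 4-week period" after the first dose. SAP Section 6.2.1 says "CH attacks will be derived from the e-diary data as described in Section 6.1.1". The content of SAP Section 6.1.1 and of SAP Appendix B, which holds the derivation logic, is blacked out in the public copy. SAP Section 6.1 lists "number of CH attacks of at least severe severity" as a baseline variable separate from the number of attacks. The SAP introduction says that the SAP prevails where the two documents differ, and SAP Section 16 reports no changes to the protocol's analyses.

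**The concern.** Section 9.5 takes over the wording of the diagnostic criterion but not the condition that makes its duration range meaningful. The range describes how long an attack lasts if left alone. Here patients may treat any attack, so a range for untreated attacks becomes a counting rule for treated ones. A real attack stopped by oxygen or medication at 10 minutes fails criterion 1.

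The objective is prevention, and an attack that happened and was aborted is not a prevented attack. The same count feeds the seven-attack entry criterion, the baseline, the primary endpoint, the 50% responder endpoint, and the week 0 to 12 and week 8 to 12 endpoints. The secondary endpoints on days with triptan or ergot use and on oxygen days describe acute treatment, but they do not return uncounted attacks to the primary count.

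**Working it through.** **The plan's own figure.** Protocol Section 9.1 has 86 evaluable patients per group, a difference of 1 attack per week, SD 2 and two-sided alpha 0.05. With the normal approximation:

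- n per arm = 2 × (1.960 + 1.282)² × 2² / 1² ≈ 84.1, rounded up to 85 (stated: 86).
- Power = Φ(1 / (2 × √(2/86)) − 1.960) = Φ(3.279 − 1.960) = 90.6% (noncentral t: 90.3%).
- Randomized: 258 / (1 − 0.14) = 300.

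The stated figures reproduce and are not in dispute.

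**Wording.** Criterion 1 of Section 9.5 and criterion B of Appendix I match in severity, location and duration. The qualifier for untreated attacks is in Appendix I and absent from Section 9.5 and the synopsis. The visible text has no rule for a treated attack shorter than 15 minutes.

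**One patient.** Suppose 10 attacks a week after dosing, 3 of them aborted before 15 minutes. The recorded count is 7. If 3 of 10 were also aborted at run-in, the baseline is 7 and the change is 0, which is correct. If none were aborted at run-in, the baseline is 10 and the recorded change is −3 with nothing prevented. The error comes from a change in the uncounted share, not from its presence.

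**Between arms.** Let P and A be the true weekly rates on placebo and active, and fP and fA the uncounted shares. The baseline term has the same expectation in each arm by randomization and drops out:

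observed difference = P(1 − fP) − A(1 − fA)

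*Equal shares, fP = fA = f.* The observed difference is (1 − f) × (P − A). The value of f is not in the documents; 5% to 30% is an assumed range. For a true difference of 1.0 and 86 per arm:

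| f | Recorded difference | Power, SD kept at 2 | n per arm for 90%, SD 2 | Power, SD scaled by 1 − f |
|---|---|---|---|---|
| 0% | 1.00 | 90.6% | 85 | 90.6% |
| 5% | 0.95 | 87.6% | 94 | 90.6% |
| 10% | 0.90 | 83.9% | 104 | 90.6% |
| 20% | 0.80 | 74.6% | 132 | 90.6% |
| 30% | 0.70 | 63.1% | 172 | 90.6% |

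*Unequal shares.* Rates and shares are assumed:

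| P | A | fP | fA | True difference | Recorded difference |
|---|---|---|---|---|---|
| 7 | 6 | 10% | 15% | 1.0 | 6.30 − 5.10 = 1.20 |
| 7 | 6 | 15% | 10% | 1.0 | 5.95 − 5.40 = 0.55 |
| 7 | 7 | 10% | 15% | 0 | 6.30 − 5.95 = 0.35 |
| 7 | 7 | 15% | 10% | 0 | 5.95 − 6.30 = −0.35 |

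**Rate at entry.** Seven attacks are required in a run-in of 7 to 10 days, and the SAP prorates the baseline to 7 days. The lowest qualifying weekly rate is therefore between 7 × 7/10 = 4.9 and 7 × 7/7 = 7.0, depending on the length of the run-in.

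**The case against.** The strongest objection is that the operative rule cannot be seen. SAP Section 6.1.1 and Appendix B are blacked out, so they cannot be called silent, and the SAP prevails. Visible SAP text suggests that criterion 1 may not be applied literally. Attacks of at least severe severity are listed apart from all attacks, and the contents entry for Section 6.4.4 grades attacks from mild to very severe. Both would be redundant if only severe attacks counted. This stands as a limit: the loss is what Section 9.5 says, not something shown to happen in the analysis. It does not clear Section 9.5. Those signs concern severity rather than duration, and SAP Section 16 declares no departure from the protocol.

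A second objection is that the rule is the same at run-in and in every blinded arm. That also stands, and it is why dilution is the likely effect. It does not remove the problem, because as-needed treatment need not stay constant. Appendix H, for example, limits butalbital and opioid days in the run-in and leaves both as needed after randomization.

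A third objection is that the planned difference and SD are already stated in terms of the defined attack, so 1.0 may be net of any loss. This is fair, and it means that the stated power is not shown to be wrong.

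Finally, counting short attacks only when treated ties the count to behaviour after randomization. If placebo patients treat more, their short attacks enter while untreated short attacks on active do not. This stands, and the fix has to deal with it.

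Two stronger readings are tempting. A reader might infer that aborted attacks are credited to the drug as prevented. The documents do not support that: it needs a larger uncounted share on active, whereas heavier acute treatment on placebo would understate the effect. A reader might also infer that the bias could match the whole planned effect. That takes a large between-arm gap in the uncounted share and a high attack rate, and the documents give neither.

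**Conclusion.** The point holds as a defect in a stated rule. Section 9.5 and the synopsis depart from the definition that the protocol reproduces in Appendix I, and read literally they discard genuine attacks aborted before 15 minutes at run-in and after dosing.

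The likely consequence is some dilution of the treatment difference. Bias arises only if the uncounted share shifts differently between arms, and its direction is open. The size cannot be determined, because no share of aborted attacks is given. Every loss figure in the working is an assumption, and the power loss in particular assumes that the SD stays at 2. Whether the analysis is affected at all depends on SAP logic that is not visible. This warrants a correction to the protocol wording and a check of the SAP. It does not support a claim that the trial is underpowered or biased towards the drug.

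**What to change.** Restore the qualifier for untreated attacks in criterion 1 of Section 9.5 and in the synopsis. State that an attack shorter than 15 minutes in which acute medication or oxygen was used counts if the other criteria are met. Apply this identically to the run-in and to every post-baseline window, and confirm that SAP Section 6.1.1 and Appendix B match.

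Add two sensitivity analyses of the primary endpoint:

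- one with the strict 15-minute floor;
- one counting all otherwise qualifying attacks shorter than 15 minutes, treated or not, because conditioning on acute use could itself differ by arm.

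The cost is about one sentence in the protocol, a matching line in the SAP derivation and two reruns. Duration, acute medication and oxygen use are already diary items. The visible text does not show whether acute use is recorded attack by attack, so this should be confirmed first. The downside is that a few brief treated headaches that were not cluster attacks may be counted, and that the count depends slightly on acute-treatment behaviour. Patient treatment does not change.

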9.5.1. Primary Endpoint

The primary efficacy endpoint of this study is the mean change from baseline (run-in period) in the weekly average number of CH attacks during the 4-week period after administration of the first dose of the IMP, ie, based on week 0 to 4 data.

9.5.2. Secondary Endpoints

The secondary efficacy endpoints to further demonstrate efficacy are as follows:

- the proportion of patients with a $\geq 50\%$ reduction from baseline (run-in period) in the weekly average number of CH attacks during the 4-week period after the first dose of the IMP, ie, based on week 0 to 4 data
- the mean change from baseline (run-in period) in the number of CH attacks during the 12-week period after administration of the first dose of the IMP, ie, based on week 0 to 12 data
- the mean change from baseline (run-in period) in the number of CH attacks during the 4-week period after administration of the third dose of the IMP, ie, based on week 8 to 12 data
- the mean change from baseline (run-in period) in the weekly average number of days with use of cluster-specific acute headache medications (triptans and ergot compounds) during the 12-week period after administration of the first dose of the IMP, ie, based on week 0 to 12 data
- the mean change from baseline (run-in period) in the weekly average number of days oxygen is used to treat ECH during the 12-week period after administration of the first dose of the IMP, ie, based on week 0 to 12 data
- assessment of patient’s perceived improvement, as measured by the PPSI at 1, 4, 8, and 12 weeks after administration of the first dose of the IMP relative to baseline (day 0)

9.5.3. Exploratory Endpoints

The exploratory efficacy endpoints of this study are as follows:

- [REDACTED]
- [REDACTED]

- [REDACTED]
- █ [REDACTED]
- █ [REDACTED]
- █ [REDACTED]
- █ [REDACTED]
- █ [REDACTED]
- █ [REDACTED]
- █ [REDACTED]
- █ [REDACTED]
- █ [REDACTED]
- █ [REDACTED]
- █ [REDACTED]
- █ [REDACTED]
- █ [REDACTED]

Wearable sensor substudy exploratory endpoints are the following:

- [REDACTED]

[REDACTED]

[REDACTED]

[REDACTED]

[REDACTED]

[REDACTED]

[REDACTED]

[REDACTED]

[REDACTED]

[REDACTED]

[REDACTED]

[REDACTED]

[REDACTED]

9.5.4. Planned Method of Analysis

The full analysis set (see Section 9.2.3) will be used for all efficacy analyses. Summaries will be presented by treatment group.

9.5.4.1. Primary Efficacy Analysis

The primary efficacy endpoint, the mean change from baseline (run-in period) in the weekly average number of CH attacks during the 4-week period after administration of the first dose of the IMP, will be analyzed using an analysis of covariance (ANCOVA). The model will include treatment, baseline number of CH attacks, baseline preventive medication use (yes or no), gender, and region (US or other).

9.5.4.2. Sensitivity Analysis

Sensitivity analysis will be conducted to explore the impact of missing data in the primary efficacy analysis. Details will be provided in the statistical analysis plan.

9.5.4.3. Secondary and Exploratory Efficacy Analysis

The continuous endpoints will be analyzed using an ANCOVA or a mixed model for repeated measures. For the proportion of responders, defined as 50% or more reduction from baseline in the weekly average number of CH attacks, data will be analyzed using a Cochran-Mantel-Haenszel test stratified by baseline preventive medication use (yes/no).

9.6. Multiple Comparisons and Multiplicity

[Redacted]

[Redacted]

[Redacted]

[Redacted]

[Redacted]

9.7. Safety Analysis

Safety analyses will be performed on the safety analysis set (Section 9.2.2). Safety assessments and time points are provided in Table 2.

All adverse events will be coded using the Medical Dictionary for Regulatory Activities. Each patient will be counted only once in each preferred term or system organ class category for the

analyses of safety. Summaries will be presented for all adverse events (overall and by severity), adverse events determined by the investigator to be related to test IMP (defined as related or with missing relationship) (overall and by severity), serious adverse events, and adverse events causing withdrawal from the study. Patient listings of serious adverse events and adverse events leading to withdrawal will be presented.

The use of concomitant medications will be summarized by therapeutic class using descriptive statistics. Concomitant medications will include all medications taken while the patient is treated with IMP.

Changes in laboratory, ECG, and vital signs measurement data will be summarized descriptively. All values will be compared with prespecified boundaries to identify potentially clinically significant changes or values, and such values will be listed.

Safety data will be summarized descriptively overall and by treatment group. For continuous variables, descriptive statistics (n, mean, SD, median, minimum, and maximum) will be provided for actual values and changes from baseline to each time point. For categorical variables, patient counts and percentages will be provided. Descriptive summaries of serious adverse events, patient withdrawals due to adverse events, and potentially clinically significant abnormal values (clinical laboratory or vital signs) based on predefined criteria will also be provided.

If any patient dies during the study, a listing of deaths will be provided, and all relevant information will be discussed in the patient narrative included in the clinical study report.

